17.1 Institutional Review Board (IRB) Approval and Consent

It is expected that the IRB will have the proper representation and function in accordance with federally mandated regulations. The IRB should approve the consent form and protocol.

In obtaining and documenting informed consent, the investigator should comply with the applicable regulatory requirement(s), and should adhere to Good Clinical Practice (GCP) and to ethical principles that have their origin in the Declaration of Helsinki.

Before recruitment and enrollment onto this study, the patient will be given a full explanation of the study and will be given the opportunity to review the consent form. Each consent form must include all the relevant elements currently required by the FDA Regulations and local or state regulations. Once this essential information has been provided to the patient and the investigator is assured that the patient understands the implications of participating in the study, the patient will be asked to give consent to participate in the study by signing an IRB approved consent form.

Prior to a patient's participation in the trial, the written informed consent form should be signed and personally dated by the patient and by the person who conducted the informed consent discussion.

17.2 Registration Procedures

Patients may not begin protocol treatment prior to registration. All patient registrations will be centralized through the Research/Nurse Coordinator of this study at the Institute for Drug Development at the Mays Cancer Center of the UT Health San Antonio. Please contact the assigned UT Health San Antonio Mays Cancer Center Research/Nurse Coordinator for questions regarding patient registration procedures.

17.3 Access to REDCAP

Enrolled study patients will be recorded in the web-based application REDCAP. Please note that a username and password is required to use this program and will be provided prior to training on the REDCAP system.

17.4 Patient Referrals to the Study

For potential patients please email the Nurse/Research Coordinator prior to consenting a patient to determine whether a slot is available on the study. In order for patient referrals to be processed efficiently, study teams are asked to inform the Nurse/Research Coordinator of any enrollment deadline date, if any.

Once a patient is referred for possible study enrollment, the treating physician will be asked to review, sign and date the study Eligibility Checklist as verification that the patient has met all inclusion/exclusion criteria. It will be the responsibility of the treating physician to issue informed consent to the patient.

17.5 Data Management and Monitoring

This study will be monitored as an Investigational Initiated study, which requires auditing after the first patient has completed 1 cycle of treatment at each site and at least an annual audit, as outlined in the Mays Cancer Center's DSMP. Please refer to *Appendix 2* for more specific details on the monitoring plan. Data submission requirements can be found in *Appendix 3*.

17.6 Adherence to the Protocol

Except for an emergency situation in which proper care for the protection, safety, and well-being of the study patient requires alternative treatment, the study shall be conducted exactly as described in the approved protocol.

17.7 Emergency Modifications

Investigators may implement a deviation from, or a change of, the protocol to eliminate an immediate hazard(s) to trial subjects without prior IRB approval.

For any such emergency modification implemented, the coordinating site must be notified of the event within five business days of making the change.

17.8 Other Protocol Deviations

According to the IRB, a protocol deviation is any unplanned variance from an IRB approved protocol that:

- 1. Is generally noted or recognized after it occurs
- 2. Has no substantive effect on the risks to research participants
- 3. Has no substantive effect on the scientific integrity of the research plan or the value of the data collected
- 4. Did not result from willful or knowing misconduct on the part of the investigator(s).

A protocol deviation is considered an instance of promptly reportable event if the occurrence:

- 1. Has harmed or increased the risk of harm to one or more research participants.
- 2. Has damaged the scientific integrity of the data collected for the study.
- 3. Results from willful or knowing misconduct on the part of the investigator(s).
- 4. Demonstrates serious or continuing noncompliance with federal regulations, State laws, or University policies.

17.9 Amendments to the Protocol

Should amendments to the protocol be required, the amendments will be originated and documented by the Principal Investigator. It should also be noted that when an amendment to the protocol substantially alters the study design or the potential risk to the patient, a revised consent form might be required. The written amendment, and if required the amended consent form, must be sent to the IRB for approval prior to implementation.

17.10 Record Retention

Study documentation includes all Case Report Forms, data correction forms or queries, source documents, Sponsor-Investigator correspondence, monitoring logs/letters, and regulatory documents (e.g., protocol and amendments, IRB correspondence and approval, signed patient consent forms).

Source documents include all recordings of observations or notations of clinical activities and all reports and records necessary for the evaluation and reconstruction of the clinical research study.

Government agency regulations and directives require that the study investigator must retain all study documentation pertaining to the conduct of a clinical trial.

17.11 Obligations of Investigators

The Principal Investigator is responsible for the conduct of the clinical trial at the site in accordance with Title 21 of the Code of Federal Regulations and/or the Declaration of Helsinki. The Principal Investigator is responsible for personally overseeing the treatment of all study patients. The Principal Investigator must assure that all study site personnel, including sub-investigators and other study staff members, adhere to the study protocol and all FDA/GCP/NCI regulations and guidelines regarding clinical trials both during and after study completion.

The Principal Investigator at each institution or site will be responsible for assuring that all the required data will be collected and entered onto the Case Report Forms. Periodically, monitoring visits will be conducted and the Principal Investigator will provide access to his/her original records or de identified documents to permit verification of proper entry of data. At the completion of the study, all case report forms will be reviewed by the Principal Investigator at each site and will require his/her final signature to verify the accuracy of the data.

17.12 Publication Policy

All potential publications and/or data for potential publications (e.g. manuscripts, abstracts, posters, clinicaltrials.gov releases) must be approved in by the PI of this study prior to release. If the investigator's wish to obtain monitored data prior to this point (or prior to the point dictated by study design), the investigator must send a written request for data to the PI of this study that includes justification. If the request is approved, data will be provided no later than 4 weeks after this request approval. The investigators are expected to use only monitored, accurate and approved data in all publications. The investigators should submit a copy of the manuscript to the biostatistician to confirm that approved data are used appropriately. Once the biostatistician gives final approval, the manuscript may be submitted to external publishers.

17.13 Pathology Requirements

Biopsy proven disease by confirmation of biopsy specimen at the treating institution pathology department is required for enrollment to the study. Biopsy material will be reviewed by the pathology department at the treating institution.

18. SAMPLES FOR BIOMARKER EVALUATION

Fresh tissue will be collected from patients with DCIS, LCIS, ALH or ADH treated with rapamycin. Tissue will be processed for IHC staining of p16, COX2, and Ki-67 in the core biopsy following the procedures described by Kerlikowske et al (66). We will also do IHC for autophagy markers, Beclin1 and LC3, and TUNEL assay to determine how rapamycin treatment may alter autophagy and apoptosis in the DCIS lesions.

To determine the effect of short-term rapamycin treatment on histopathological biomarkers in DCIS. A pathologist will quantify histopathological parameters including lesion size, nuclear grade, and presence of necrosis in each patient's surgical specimens, as well as IHC for the markers including p16, COX2, and Ki-67.

Three specific parameters will be evaluated:

- 1. Luminal-to-basal epithelial ratio, which will examine the MaSC in both luminal and basal cells, and their ratio, in order to address whether this ratio will change during aging;
- 2. Basal and luminal stem/progenitor cell frequency, which will examine the percentage of cells that are capable forming spheres, and whether these frequencies will change during aging; and
- 3. 3D structure regeneration frequency in serial passages, which will examine the selfrenewal/regeneration capacity of the stem and progenitor cells that are capable of forming spheres in suspension culture and in 3D-ECM culture, and can re-form the spheres when the sphere-forming cells are dissociated and allowed to regenerate spheres.

All fresh tissue specimens will be delivered to [name] laboratory located at:

UT Health San Antonio [name] [contact]

APPENDIX 1 – Common Toxicity Criteria for Adverse Events

Toxicity will be graded according to the NCI's Common Toxicity Criteria for Adverse Events (CTCAE) version 4.03. The CTCAE version 4.03 can be accessed at the following link: http://evs.nci.nih.gov/ftp1/CTCAE/CTCAE 4.03 2010-06-14 QuickReference 5x7.pdf

APPENDIX 2 – Data Safety & Monitoring Plan

a. Data and Safety Monitoring Oversight

A Data and Safety Monitoring Plan is required for all individual protocols conducted at UT Health San Antonio Mays Cancer Center. All protocols conducted at UT Health San Antonio Mays Cancer Center are covered under the auspices of the UT Health San Antonio Mays Cancer Center Institutional Data Safety Monitoring Plan (DSMP).

The UT Health San Antonio Mays Cancer Center Institutional DSMP global policies provide individual trials with:

- 1. institutional policies and procedures for institutional data safety and monitoring,
- 2. an institutional guide to follow,
- 3. monitoring of protocol accrual by the UT Health San Antonio Mays Cancer Center Protocol Review Committee,
- 4. review of study forms and orders by the Forms Committee,
- 5. tools for monitoring safety events,
- 6. independent monitoring and source data verification by the UT Health San Antonio Mays Cancer Center QA Monitor/Auditor
- 7. monitoring of UPIRSO's by the Director of Quality Assurance and DSMC,
- 8. determining level of risk (Priority of Audit Level Score PALS),
- 9. oversight by the Data Safety Monitoring Committee (DSMC), and
- 10. Verification of protocol adherence via annual audit for all Investigator Initiated Studies by the UT Health San Antonio Mays Cancer Center Quality Assurance Division.

b. Monitoring Progress and Safety

Due to the risks associated with participation in this protocol, the UT Health San Antonio Mays Cancer Center DSMB #2 in conjunction with the Principal Investigator will perform assessment of adverse events, adverse event trends and treatment effects on this study. The UT Health San Antonio Mays Cancer Center DSMB #2 acts as an independent Data Safety Monitoring Board (DSMB) for IIS conducted at UT Health San Antonio Mays Cancer Center. The UT Health San Antonio Mays Cancer Center. The UT Health San Antonio Mays Cancer Center. The UT Health San Antonio Mays Cancer Center DSMB #2 will monitor data throughout the duration of a study to determine if continuation of the study is appropriate scientifically and ethically. An additional layer of review is provided by the UT Health San Antonio Mays Cancer Center Data Safety Monitoring Committee (DSMC) who will review DSMB quarterly reports. Monitoring will be conducted every 12 months from the initiation of the study until the last enrolled patient has had the end of study visit.

Baseline adverse events and serious adverse events will be captured using the UT Health San Antonio Mays Cancer Center Master Adverse Events Document (or proper AE tracking mechanism as per Clinical Trial Office policy) for each patient using CTCAE V. 4.03 for the grading and attribution of adverse events (*Appendix 1*).

Usage of the UT Health San Antonio Mays Cancer Center Master Adverse Events Document (or proper AE tracking mechanism as per Clinical Trial Office policy) centrally documents:

- 1. the event and grades the seriousness of the event,
- 2. if the event was a change from baseline,
- 3. the determination of the relationship between the event and study intervention,
- 4. if the event was part of the normal disease process, and

5. What actions were taken as a result of the event.

c. Safety Definitions

For this study, the following safety definitions will be applicable:

Adverse Event Definition: An adverse event (AE) is defined as any untoward or unfavorable medical occurrence in a human subject, including any abnormal sign (for example, abnormal physical exam or laboratory finding), symptom, or disease, temporally associated with the subject's participation in the research, whether or not considered related to the subject's participation in the research. For this study, all adverse events will be documented starting with day 7 and ending 30 days after the last dose of study drug is received.

Serious Adverse Event Definition: A serious adverse event (SAE) is defined as any adverse event that:

- 1. results in death;
- 2. is life-threatening (places the subject at immediate risk of death from the event as it occurred);
- 3. results in inpatient hospitalization or prolongation of existing hospitalization;
- 4. results in a persistent or significant disability/incapacity;
- 5. results in a congenital anomaly/birth defect; or
- 6. based upon appropriate medical judgment, may jeopardize the subject's health and may require medical or surgical intervention to prevent one of the other outcomes listed in this definition

Unanticipated Problems Involving Risks to Subjects or Others Definition: Unanticipated problem involving risk to subjects or others includes any incident, experience or outcome that meets all of the following criteria:

unexpected (in terms of nature, severity, or frequency) given (a) the research procedures that are described in the protocol-related documents, such as the IRB-approved research protocol and informed consent document; and (b) the characteristics of the subject population being studied (note: the unfounded classification of a serious adverse event as "anticipated" constitutes serious non-compliance); definitely related or probably related to participation in the research; and suggests that the research places subjects or others at a greater risk of harm (including physical, psychological, economic, or social harm) than was previously known or recognized

d. Reporting Requirements

For this study, the Master Adverse Events Documents collected on patients for this protocol will be reviewed by the PI on a monthly basis to determine if a serious safety problem has emerged that result in a change or early termination of a protocol such as:

- 1. dose modification,
- 2. suspending enrollment due to safety or efficacy, or
- 3. termination of the study due to a significant change in risks or benefits.

AE's and SAE events that occur during clinical trials with or without an Investigational New Drug (IND) application are mandatory reports submitted to FDA via **Medwatch FDA F3500A within 15 days for events that have at least a possible relationship with the drug.**

e. Assuring Compliance with Protocol and Data Accuracy

As with all studies conducted at UT Health San Antonio Mays Cancer Center, the PI has ultimate responsibility for ensuring protocol compliance, data accuracy/integrity and responding to recommendations that emanate from monitoring activities. The research site will be audited for accuracy at the end of the treatment cycle for the first patient enrolled. Protocol compliance, data accuracy and reporting of events is further ensured by an annual audit conducted by the Data Safety Officer, whose audit report is shared with the PI, the research team, and will be reviewed by the UT Health San Antonio Mays Cancer Center DSMB.

f. UT Health San Antonio Mays Cancer Center DSMB Membership

The UT Health San Antonio Mays Cancer Center has two DSMB's with a primary set of members specific to the histology of the study consisting of UT Health San Antonio faculty and staff. This Protocol is under the jurisdiction of DSMB#2 for Solid Tumor Studies.

As per NCI guidelines and to eliminate conflict of interest (financial, intellectual, professional, or regulatory in nature), the UT Health San Antonio Mays Cancer Center DSMB specific to this study will not treat patients on this protocol. Usage of the DSMB specific to the histology has been created to ensure that experts in that histology are represented on the DSMB assembled for this protocol, but may be expanded, at the Pl's discretion, to include other members which may include:

- 1. experts in the fields of medicine and science that are applicable to the study (if not currently represented on the DSMB),
- 2. statistical experts,
- 3. lay representatives,
- 4. multidisciplinary representation, from relevant specialties including experts such as bioethicists, biostatisticians and basic scientists, and
- 5. others who can offer an unbiased assessment of the study progress.

Additional or alternate membership of in the DSMB is selected by the DSMC chair, in conjunction with the PI of this protocol.

g. UT Health San Antonio Mays Cancer Center DSMB Charter and Responsibilities

The UT Health San Antonio Mays Cancer Center DSMB will provide information on the membership composition, including qualifications and experience to both the UT Health San Antonio IRB and UT Health San Antonio Mays Cancer Center PRC for review. The UT Health San Antonio Mays Cancer Center DSMB for this study will act as an independent advisory board to the PI and will report its findings and recommendations to the PI, the UT Health San Antonio IRB and the UT Health San Antonio Mays Cancer Center DSMC. UT Health San Antonio Mays Cancer Center DSMB reports will utilize the Investigator Initiated Study Quarterly DSMB Report Form and meetings will occur on a monthly basis to review any updates from the prior meeting.

Once the protocol is activated, if not already established elsewhere in the protocol the UT Health San Antonio Mays Cancer Center DSMB will establish and provide:

- 1. procedures for maintaining confidentiality;
- 2. statistical procedures including monitoring guidelines, which will be used to monitor the identified primary, secondary, and safety outcome variables;
- 3. consider factors external to the study when relevant information becomes available, such as scientific or therapeutic developments that may have an impact on the safety of the participants or the ethics of the study;

- 4. plans for changing frequency of interim analysis as well as procedures for recommending protocol changes;
- 5. recommendation of dose escalation, MTD recommendation of early termination based on efficacy results;
- 6. recommendation of termination due to unfavorable benefit-to-risk or inability to answer study questions;
- 7. recommendation of continuation of ongoing studies;
- 8. recommend modification of sample sizes based on ongoing assessment of event rates; and
- 9. review of the final results and publications.

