6. TREATMENT PLAN

This is a phase II window of opportunity trial in which women with a diagnosis of DCIS, LCIS, ALH or ADH will be treated with rapamycin at 2 mg/day for 5-7 days. Surgery will be performed 3-7 days after the last dose of rapamycin. An evaluable patient for toxicity is any patient who has received at least 1 dose of rapamycin. An evaluable patient for efficacy is any patient who has completed at least 5 days of rapamycin therapy and has had surgery within the 7-day window.

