12. FOLLOW-UP POST-THERAPY

Patients will be followed 3 months after surgery at the time of routine clinic visit or via phone call with study personnel, See APPENDIX 3 –subsection titled Research Chart (case report form needed for data collection during this 3-month follow-up visit).

Treatment after study completion will be left to the discretion of the treating physician(s) and will not be considered part of this study. However, patients should still be followed for surgical complications as part of their standard of care.

Procedures	Screening & Baseline	Day 1-7 ⁴	Day before Surgery	Surgery ²	3 month Follow-Up
Tissue procurement ¹				Х	
Informed consent	х				
Rapamycin administration		Х			
Cancer history ³	х		х		
Physical exam ³	х		х		
CBC w/ diff	X ³		Х		
Comprehensive metabolic panel	X ³		х		
Lipid panel	х		х		
Estradiol ⁵	Х		х		
FSH⁵	Х		х		
Toxicity (AE) assessment			Х		Х

13. SCHEDULE OF EVENTS

¹ Fresh tissue procurement will be required for study purposes.

² Surgery can take place 3-7 days after completion of rapamycin treatment

- ³ Pre-study laboratory tests, cancer history, and physical exam (including review of systems) must be completed within 28 days prior to registration. At the discretion of the treating physician and only if clinically indicated as part of their standard of care, the pre-study CBC and CMP will be repeated one (1) day prior to treatment administration.
- ⁴ Rapamycin will be administered for 5-7 days
- ⁵ Estradiol and FSH are required only if patient is under 60 years of age and has not had a bilateral oophorectomy.

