16. ADVERSE EVENTS REPORTING

Adverse event data collection and reporting, which are required as part of every clinical trial, are done to ensure the safety of subjects enrolled in the studies as well as those who will enroll in future studies using similar agents. Subjects must be carefully monitored for AEs. Adverse events should be assessed in terms of their seriousness, intensity, and relationship to the study drug. Adverse events are reported in a routine manner at scheduled times during a trial. Additionally, certain adverse events must be reported in an expedited manner to allow for optimal monitoring of patient safety and care.

All patients experiencing an adverse event, regardless of its relationship to study drug, will be monitored until:

- 1. the adverse event resolves or the symptoms or signs that constitute the adverse event return to baseline;
- 2. there is a satisfactory explanation other than the study drug for the changes observed; or
- 3. death occurs.

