16.1 Definitions & Descriptions

16.1.1 Adverse event (AE)

An adverse event (AE) is any untoward medical occurrence in a patient receiving study treatment and which does not necessarily have a causal relationship with this treatment. An AE can, therefore, be any unfavorable and unintended sign (including an abnormal laboratory finding), symptom, or disease temporally associated with the use of an experimental intervention, whether or not related to the intervention. A "drug-related toxicity" includes as events, any toxicity considered related, probably related, or possibly related to study drugs. Toxicities clearly not related to the drug, such as disease progression, environmental, unrelated trauma may not be considered "drug related toxicity".

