16.1.3 Serious Adverse events

All SAEs, regardless of attribution, occurring during the study or within 30 days of the last administration of study drug must be reported upon discovery or occurrence. Additional expedited or routine reporting may be required, depending on the nature of the SAE. A "serious" adverse event is defined in regulatory terminology as any untoward medical occurrence that:

- 1. Results in death. If death results from (progression of) the disease, the disease should be reported as the event (SAE) itself.
- 2. Is life-threatening. The patient was at risk of death at the time of the event; it does not refer to an event that hypothetically might have caused death if it were more severe.
- 3. Requires in-patient hospitalization or prolongation of existing hospitalization for \ge 24hours.
- 4. Results in persistent or significant disability or incapacity.
- 5. Is a congenital anomaly/birth defect.
- 6. Is an important medical event.
- 7. Any event that does not meet the above criteria, but that in the judgment of the investigator jeopardizes the patient, may be considered for reporting as a serious adverse event. The event may require medical or surgical intervention to prevent one of the outcomes listed in the definition of "Serious Adverse Event". Examples: allergic bronchospasm requiring intensive treatment in an emergency room or at home; convulsions that may not result in hospitalization; development of drug abuse or drug dependency.

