16.2 Adverse event reporting

Steps to determine if expedited reporting is required include all events that occur within 30 days of the last dose of protocol treatment. Any event that occurs more than 30 days after the last dose of treatment

and is attributed (possibly, probably, or definitely) to the agent, must also be reported accordingly. You are required to:

- 1. **Identify** the type of adverse event using the NCI CTCAE v 4.03.
- 2. **Grade** the adverse event using the NCI CTCAE v 4.03.
- 3. **Determine** whether the adverse event is related to the protocol therapy.

Attribution categories are as follows:

Definite: AE is clearly related to the study treatment (attribution should be separated by each study drug) **Probable:** AE is likely related to the study treatment (attribution should be separated by each study drug) **Possible:** AE may be related to the study treatment (attribution should be separated by each study drug) **Unrelated:** AE is clearly NOT related to the study treatment (attribution should be separated by each study drug) study drug

Determine the prior experience of the adverse event. Expected events are those that have been previously identified as resulting from administration of the specific agent. An adverse event is considered unexpected, for expedited reporting purposes only, when either the type of event or the severity of the event is not listed in the current protocol and/or the drug package insert.

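### Appendix 2(c) starts adverse-event documentation on day 7 of a 5-7 day course, so short-lived non-serious events during dosing could go unrecorded

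*Combined protocol and SAP*

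**What the plan says.** Appendix 2(c) gives a documentation window, framed as specific to this study: "all adverse events will be documented starting with day 7 and ending 30 days after the last dose of study drug is received". It is the only sentence in the document that gives a start day for documenting adverse events.

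The rest of the plan bears on it as follows.

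- Toxicity is the first secondary objective (Section 4.2). Section 6 sets the population: "An evaluable patient for toxicity is any patient who has received at least 1 dose of rapamycin".
- Dosing lasts 5-7 days (Sections 6 and 11) and occupies the Day 1-7 column of the Schedule of Events (Section 13).
- In that Schedule the row "Toxicity (AE) assessment" is blank for Day 1-7. It is marked only for the day before surgery and for the 3-month follow-up. Footnote 2 reads: "Surgery can take place 3-7 days after completion of rapamycin treatment".
- Section 16 opens with "Subjects must be carefully monitored for AEs" and has every patient with an AE followed until resolution, another satisfactory explanation, or death. Section 16.1.1 defines an AE as "any untoward medical occurrence in a patient receiving study treatment". Neither carries a day-7 start.
- Section 16.2: "Steps to determine if expedited reporting is required include all events that occur within 30 days of the last dose of protocol treatment".
- Section 16.6 sends all remaining AEs to the eCRF at the times set by the Schedule.
- Section 16.1.3 has a separate rule for serious events: "All SAEs, regardless of attribution, occurring during the study or within 30 days of the last administration of study drug must be reported".
- Appendix 3 has the Master Adverse Event Form submitted within 5 days of the first dose, showing events present at baseline.

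**The concern.** A toxicity result should cover the time on drug. Taken at face value, Appendix 2(c) opens the recording window when dosing is finished or on its last day. A non-serious event that starts on day 2 and clears by day 5 would then fall outside the documented period, although the patient counts in the toxicity denominator. This matters most for someone who stops after one to four doses: every dosing day precedes the window, and a transient event that led to the stop might not be on the form.

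Two things are at stake. One is the descriptive toxicity result, which would be understated. The other is ongoing oversight: under Appendix 2 the PI reviews the AE forms monthly and the DSMB assesses AE trends, and both would work from the same incomplete record. Annual audit would not catch the omission, because leaving out day 1-6 events would comply with Appendix 2(c) as written.

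**Working it through.** No sample size, power or error rate is involved. The check is a day count and a comparison of sections.

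**Inputs.** Day 1 is the first dose (the Schedule places administration under Day 1-7). L is the number of daily doses, 5 to 7 for a full course (Section 6). Surgery falls 3-7 days after the last dose (Section 6; Schedule footnote 2). The window runs from day 7 to 30 days after the last dose (Appendix 2(c)).

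**Formulas.** Dosing days before day 7 = min(6, L). Window end = day L + 30. Surgery = day L + 3 to L + 7, so the day-before visit = day L + 2 to L + 6.

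| L | Dosing days before day 7 | Window end | Days from first dose to window end | Days from day 7 to window end | Share missed (days 1-6) | Day-before-surgery visit |
|---|---|---|---|---|---|---|
| 5 | 5 of 5 | day 35 | 35 | 29 | 6/35 = 17.1% | day 7-11 |
| 6 | 6 of 6 | day 36 | 36 | 30 | 6/36 = 16.7% | day 8-12 |
| 7 | 6 of 7 | day 37 | 37 | 31 | 6/37 = 16.2% | day 9-13 |

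For early stops, L = 1, 2, 3, 4 gives 1 of 1, 2 of 2, 3 of 3 and 4 of 4. No visit day is computed for these patients, because the plan does not state when surgery follows an early stop.

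The first scheduled AE assessment is therefore on day 7-13. That is 6-12 days after the first dose and 2-6 days after the last.

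**Two readings of day 7.**

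1. *Onset cut-off.* Events starting on days 1-6 are outside the window, and the counts in the table apply. This conflicts with Sections 6, 16, 16.1.1, 16.2 and 16.6, which imply coverage from the first dose without stating a start day.
2. *Start of recording.* Day 7 is the earliest day on which the day-before-surgery visit can fall (L = 5, surgery on day 8), so the sentence agrees with the Schedule. The onset counts then do not measure a loss. What remains is that no text says the visit asks about events since the first dose.

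**Does another section close the gap?** Section 16.6 refers routine AEs to the Schedule, which has no mark in the dosing column. Section 16.2 concerns expedited reporting and gives an end but no start. Appendix 3's early form covers baseline events only. Its later form is tied to an end-of-treatment visit that the Schedule does not list, and it too gives no onset start. None of these settles the matter for routine non-serious events.

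**The case against.** The strongest reply is that Appendix 2(c) speaks of when events are documented, not of when they must begin, and that day 7 matches the earliest first AE assessment. On that reading the sentence restates the Schedule. The body text also leaves no class of AE exempt: Section 16.2 takes in all events up to 30 days after the final dose for the expedited-reporting decision, Section 16.6 sends the remainder to the eCRF, and Section 16 follows every AE to an outcome with no onset limit. The AE form is already open before day 7. The day-before-surgery visit includes a physical exam as well as CBC, metabolic and lipid panels; the exam's footnote mentions a review of systems, although it is worded for the pre-study exam. Day 7 may also be a typing or extraction slip.

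Much of this stands. The recording reading is open, ongoing events and most laboratory changes would be seen at that visit, and earlier events may be recalled there. It does not remove the point, because under either reading nothing instructs staff to ask about days 1-6, and the only stated start day is one that most patients following the 5-7 day range literally would reach at or after the end of dosing.

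A reader might go further and infer that on-treatment toxicity will be lost, or that serious events are affected. The documents do not support either. Recall at the visit is plausible, and serious events are reportable throughout the study under Sections 16.1.3 and 16.3. A reader might also see a conflict between the 30-day end and the 3-month toxicity assessment. Section 16.2 partly answers that, since later events attributed to the drug must still be reported, so it is not pressed here.

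**Conclusion.** Appendix 2(c) is wrong as written, at low severity. Under the onset reading it leaves out 5 of 5, 6 of 6 or 6 of 7 dosing days, which is 16-17% of the days from first dose to 30 days after the last. Under the recording reading it agrees with the Schedule but leaves the look-back of the first AE assessment unstated.

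The exposure is confined to non-serious events that begin and resolve before day 7 and are not elicited on the day before surgery. It touches the descriptive toxicity result and the AE forms that the PI and DSMB review. Section 15 specifies no toxicity test or threshold, so no inferential result changes.

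The conclusion assumes that day 1 is the first dose and that day 7 is what the source protocol says. The figures are days, not events; the number of events lost cannot be derived from the documents.

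**What to change.** 1. Check day 7 in Appendix 2(c) against the source protocol.
2. Unless it proves to be a typing or extraction slip, amend the sentence so that AEs with onset from the first dose to 30 days after the last dose are documented. Baseline conditions continue to be recorded beforehand, as Appendix 3 already provides.
3. In either case, add a footnote to the Schedule of Events stating that the existing day-before-surgery AE assessment elicits all events since the first dose.

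The cost is one sentence and one footnote. No visit is added, and the extra work is at most a few more entries per patient on a form already in use.
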